## 7.9 *Safety analysis*

All safety analyses will be performed on subjects of the Safety set. Subjects will be analysed according to the treatment they actually received.

### 7.9.1 *Local Skin Reactions (LSRs)*

LSRs (telangiectasia, skin atrophy, striae rubrae, erythema, edema, scaling/dryness, stinging/burning, and pruritus) will be listed separately for face and trunk ([Listing 16.2.9.1](#), [Listing 16.2.9.2](#)) and summarized separately for face and trunk by the frequency of each individual LSR and severity at each visit ([Table 14.3.5.1](#), [Table 14.3.5.2](#)).

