10.2 Local Skin Reactions (LSRs)

At every in-clinic study visit and unscheduled visits, the investigator or designee will document the severity of the following LSRs known to be associated with application of topical steroids in the treatment areas (face and trunk, separately):

- Telangiectasia
- Skin atrophy
- Striae rubrae

A five-point ordinal scale will be used to assess the severity of these reactions (0=none, 1=trace, 2=mild, 3=moderate, and 4=severe).

In addition, the investigator or designee will evaluate the severity of the following LSRs known to be associated with acne vulgaris in the treatment areas (face and trunk, separately), using the five-point ordinal scales described below:

- Erythema
- Edema
- Scaling/dryness

Erythema:

0	None
1	Minimal – barely perceptible erythema
2	Mild – predominantly minimal erythema (pink) in the treated area with or without a few isolated areas of more intense erythema
3	Moderate – predominantly moderate erythema (red) in the treated area with or without a few isolated areas of intense erythema (bright red)
4	Severe – predominantly intense erythema (bright red) in the treated area with or without a few isolated areas of very intense (fiery red) erythema

Edema:

0	None
1	Minimal – scant, rare edema
2	Mild – easily seen edema, minimally palpable, involving up to 1/3 of the Treatment Area
3	Moderate – easily seen edema and typically palpable, involving between 1/3 to 2/3 of the Treatment Area
4	Severe – easily seen edema, indurated in some areas, involving over 2/3 of the Treatment Area

Scaling/dryness:

0	None
1	Minimal – barely perceptible desquamation
2	Mild - limited areas of fine desquamation in up to 1/3 of the treatment area
3	Moderate – fine desquamation involving 1/3 to 2/3 of the treatment area or limited areas of coarser scaling
4	Severe – coarser scaling involving more than 2/3 of the treatment area or limited areas of very coarse scaling

In addition, subjects will be asked to rate the severity of the following LSRs that occurred in the treatment areas (face and trunk, separately) since the last visit, using the four-point ordinal scales described below:

- Stinging/burning
- Pruritus

Stinging/burning:

0	None
1	Minimal, barely perceptible – tolerable and little discomfort
2	Moderate – tolerable, but causes some discomfort
3	Severe – very uncomfortable or intolerable

Pruritus (itching):

0	None - no evidence of itching

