1	Mild - only aware of itching at times, only present when relaxing, not present when focused on other activities
2	Moderate - often aware of itching, annoying, sometimes disturbs sleep and daytime activities
3	Severe -constant itching, distressing; frequent sleep disturbance, interferes with activities

These LSRs will be collected independently of AEs. Only LSRs that require medical intervention (e.g., prescription medication) or require withholding the application of the test articles will be documented as AEs. Any LSRs that are not listed above will be recorded as AEs.

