17.2 Endpoints

17.2.1 Safety Endpoints

Safety endpoints will include:

- Incidence of any local and systemic treatment emergent AEs (TEAEs).
- Number of subjects with presence (and severity) of each individual LSR (telangiectasia, skin atrophy, striae rubrae, erythema, edema, scaling/dryness, stinging/burning, and pruritus) for each treatment area, as applicable, at each time point collected (Baseline, and LTF-Months 1, 3, 6, and 9, and any Unscheduled Visits).
- UPT results in all WOCBP at Baseline, LTF-Month 6, and EOS.

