17.3.1 Safety Analyses

Extent of Exposure

Descriptive statistics will be used to summarize exposure to test article for the Safety, ITT, and PP sets. The total amount of test article used (grams applied) will be calculated for each subject from the weights of the returned test articles. The mean daily amount of test article applied (total amount of test article used/number of days of treatment) will be calculated for each subject. The number of applications and days dosed for each treatment area (face and/or trunk from Subject Diary) will also be summarized.

Local Skin Reactions (LSRs)

LSRs (telangiectasia, skin atrophy, striae rubrae, erythema, edema, scaling/dryness, stinging/burning, and pruritus) will be summarized by the frequency of each individual LSR and severity at each clinic visit for face and trunk, separately.

Adverse Events (AEs)

AEs will be coded using the MedDRA coding dictionary summarized by relationship to test article and severity.

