- 8 If truncal acne is to be treated (as designated by the investigator AND desired by subject), identify the percent body surface area (BSA) to be treated. BSA was estimated based on the assumption that 1% BSA is equivalent to the area of the subject's hand with fingers held together.
- 9 LSRs assessed at the EOS Visit of the Phase 3 pivotal trial (Visit 4-Pivotal) were used as pre-application data for face. LSRs [pre-application] were assessed for trunk at Visit 4-LTF. After ITA application in the clinic, LSRs were assessed post-application (Visit 4-LTF) for face and trunk, as applicable.
- 10 Any ongoing concomitant medications and procedures were reviewed at Visit 4-LTF.
- 11 Instruct subject (and parent/guardian, if applicable) on ITA application and provide instruction sheet. Review compliance with respect to the amount and number of doses applied since the last visit.
- 12 Dispense subject diary, as needed.

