## 6. STATISTICAL CONSIDERATIONS

### 6.1 Study Endpoints

#### 6.1.1 Safety Endpoints

Safety endpoints will include:

- Incidence of any local and systemic treatment emergent AEs (TEAEs).
- Number of subjects with presence (and severity) of each individual LSR (telangiectasia, skin atrophy, striae rubrae, erythema, edema, scaling/dryness, stinging/burning, and pruritus) for each treatment area, as applicable, at each time point collected (Baseline, and LTF-Months 1, 3, 6 and 9, and any Unscheduled Visits).
- UPT results in all WOCBP at Baseline, LTF-Month 6 and EOS.

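### Local skin reactions are planned only as severity frequencies by visit, so no described output gives the number of subjects with a new or worsened reaction

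*SAP*

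**What the plan says.** SAP 6.1.1 defines the LSR endpoint as the "Number of subjects with presence (and severity) of each individual LSR", by treatment area, "at each time point collected (Baseline, and LTF-Months 1, 3, 6 and 9, and any Unscheduled Visits"). Protocol 17.2.1 has the same definition. For the analysis, Protocol 17.3.1 states that LSRs "will be summarized by the frequency of each individual LSR and severity at each clinic visit for face and trunk, separately". In SAP 7.9.1 they are listed by subject for each area and "summarized separately for face and trunk by the frequency of each individual LSR and severity at each visit".

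Baseline scores are available. The SAP Study Schedule notes state that "LSRs assessed at the EOS Visit of the Phase 3 pivotal trial (Visit 4-Pivotal) were used as pre-application data for face". For the trunk, a pre-application score is taken at Visit 4-LTF, and a post-application score is taken at that visit for both areas where cream is applied.

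The link to adverse events is set in Protocol 10.2 and repeated in SAP 3.2: "Only LSRs that require medical intervention (e.g., prescription medication) or require withholding the application of the test articles will be documented as AEs". SAP 7.9.2 gives per-subject counts of AEs that begin or worsen after the first dose. SAP 7.4 does not replace missing data.

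**The concern.** Long-term safety is the primary objective, and LSRs form one of three safety endpoints. Protocol 10.2 links telangiectasia, skin atrophy and striae rubrae to topical steroids, and Protocol 14.1 says that all three have been reported with CB-03-01 creams. A natural question for a study of up to 12 months of exposure is how many subjects develop one of these, or see one get worse. A by-visit frequency table does not answer it, because it does not follow the same subject from baseline through the later visits.

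The issue also affects erythema, edema and scaling/dryness, which Protocol 10.2 describes as "LSRs known to be associated with acne vulgaris in the treatment areas". Their group frequency can stay level or fall as acne improves while other subjects develop new reactions. Unscheduled visits are part of the endpoint, but no rule brings their scores into a per-subject result. By-visit denominators can also shrink as subjects leave.

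**Working it through.** **1. The plan's own figures.** None is given for LSRs. The only precision figures (Protocol 17.1, SAP 6.3) concern important AEs and use p + 1.96 × √(p(1 − p)/n) with p = 0.01:

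- n = 100: 0.01 + 0.0195 = 2.95%, stated as 3%.
- n = 300: 0.01 + 0.0113 = 2.13%, stated as 2.1%.

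Both reproduce, and neither bears on this point.

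**2. What a by-visit table determines.** For one LSR in one area, let b be the proportion affected at Baseline and m₁ to m₄ the proportions at LTF-Months 1, 3, 6 and 9, with complete data. If only these are known:

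- proportion ever affected after baseline: from max(m) to min(1, Σm);
- proportion unaffected at baseline and affected later: from max(0, max(m) − b) to min(1 − b, Σm).

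The same bounds apply at any severity cut, reading affected as at or above that grade. Tabulating severity therefore does not remove the uncertainty.

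**3. Illustration.** The documents give no LSR rates, so every rate below is assumed. The base of 600 is the protocol's approximate enrolment (the SAP reports 609).

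| Baseline b | Each of 4 visits | Newly affected | Of 600 |
|---|---|---|---|
| 0% | 5% | 5% to 20% | 30 to 120 |
| 5% | 5% | 0% to 20% | 0 to 120 |
| 10% | 10% | 0% to 40% | 0 to 240 |
| 20% | 20% | 0% to 80% | 0 to 480 |

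In the first row the lower limit means the same subjects at every visit, and the upper limit (4 × 5%) means different subjects each time. Independent visits give 1 − 0.95⁴ = 18.5%. The planned table shows 5% at each visit in all three cases.

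**4. Whether the AE tables close the gap.** An LSR that leads to medical intervention or withheld cream is recorded as an AE and then enters the per-subject counts of SAP 7.9.2. Any other listed LSR stays out. Under this rule a new grade 3 skin atrophy that is only observed would appear in the by-visit table and the listing, and in no per-subject count.

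**The case against.** The strongest reply is that the SAP analyses the endpoint as the protocol defines it, in a descriptive study with no hypothesis test, and that the LSRs with consequences are already counted as TEAEs. Protocol 6.3 tells subjects to stop the cream and contact the site if irritation or rash develops, which feeds that route. Protocol 14.1 reports earlier LSRs as mostly minimal to mild, with no discontinuations because of them. All of this is correct. It limits the gap to reactions below the AE threshold, but does not close it.

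A reader might infer four stronger things that the documents do not support:

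- That only presence is reported. Severity is part of both the endpoint and the summary.
- That baseline is ignored. Baseline is a tabulated time point, so group distributions can be compared by eye; only the within-subject comparison is missing.
- That the study could never give the number. Scores are listed per subject, so it can be derived without new data.
- That a shift from baseline would separate drug from disease. This is a single-arm, open-label study of a fluctuating condition; cream may be stopped and restarted by area, and some acne cleansers are allowed. A shift table counts change and cannot say what caused it.

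Two further objections stand. The illustrative rates are assumptions and do not show the size of any error in this trial. Counting every 0-to-1 step as worsening would also gather rating noise over several visits, so a higher threshold is needed beside it.

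**Conclusion.** The point holds as a gap in the planned analysis. The SAP text describes no output that gives, per subject, the number with a new or worsened LSR. By-visit frequencies leave that number undetermined over a wide range (5% to 20% in the first row of the illustration). The largest by-visit figure can understate the proportion ever affected; whether it does depends on how far reactions persist in the same subjects, which the documents do not say.

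This rests on the SAP text alone. The table shells (SAP Appendix 1) are not in the text available, so a shift or any-post-baseline row in Tables 14.3.5.1 and 14.3.5.2 cannot be excluded. Data collection and sample size are unaffected. The change is worth making because the reactions tied to topical steroids are central to the safety question and the data are already held.

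**What to change.** In SAP 7.9.1 add, for each LSR and each treatment area:

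- (a) worst post-baseline severity per subject over all scheduled and unscheduled visits, cross-tabulated against the pre-application baseline grade;
- (b) the number and percentage of subjects with a new or worsened LSR, shown as any grade increase, as worsening to grade 2 or higher, and as worsening to grade 3 or higher, with telangiectasia, skin atrophy and striae rubrae first. Label the cuts by scale: grades 2 and 3 mean mild and moderate on the five-point scales, but moderate and severe on the four-point scales for stinging/burning and pruritus.

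Define the baseline:

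- Face: Visit 4-Pivotal.
- Trunk: the pre-application score at the visit where trunk treatment first starts, as the protocol synopsis (Study Measurements) does for IGA. Show subjects without such a score as missing baseline.
- Report the Visit 4-LTF post-application score separately and do not use it as baseline.

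Add two statements. The face baseline follows 0 or 3 months of active cream, so reactions that began in the pivotal study are not counted as new. The shift describes change and does not attribute it to the drug.

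The cost is SAP wording and two more tables from existing data, with no new assessments. The downside is that the percentage of subjects with any post-baseline LSR will be at least as high as any by-visit figure in the same subjects, and part of it will reflect acne fluctuation and rating noise.

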### 7.9.2 *Adverse events*

All AEs will be coded using the Medical Dictionary for Regulatory Activities (MedDRA) and listed. The version of the dictionary used for coding will be reported in the clinical study report.

Individual TEAEs (i.e. all the all AEs occurring or worsening after the first dose of the test article) will be listed ([Listing 16.2.7.1](#)).

TEAEs will be summarised as follows:

- The number and percentage of subjects with any TEAE and the number of TEAEs will be presented overall ([Table 14.3.1.1](#)) and by SOC and PT ([Table 14.3.1.2](#));
- The number and percentage of subjects with any TEAE by relationship and the number of TEAEs by relationship will be presented ([Table 14.3.1.1](#));
- The number and percentage of subjects with any TEAE related to the IMP and the number of TEAEs related to the IMP will be presented by SOC and PT ([Table 14.3.1.3](#));
- The number and percentage of subjects with any TEAE by severity and the number of TEAEs by severity will be presented overall ([Table 14.3.1.1](#)) and by SOC and PT ([Table 14.3.1.4](#));
- The number and percentage of subjects with any TEAE leading to discontinuation and the number of TEAEs leading to discontinuation will be presented ([Table 14.3.1.1](#)).

Serious TEAEs will be summarised as follows:

- The number and percentage of subjects with any Serious TEAE and the number of Serious TEAEs will be presented overall (Table 14.3.1.1) and by SOC and PT (Table 14.3.1.5);
- The number and percentage of subjects with any Serious TEAE by relationship and the number of Serious TEAEs by relationship will be presented (Table 14.3.1.1);
- The number and percentage of subjects with any Serious TEAE related to the IMP and the number of Serious TEAEs related to the IMP will be presented by SOC and PT (Table 14.3.1.6);
- The number and percentage of subjects with any Serious TEAE leading to discontinuation and the number of Serious TEAEs leading to discontinuation will be presented (Table 14.3.1.1).
- The number and percentage of subjects with any Serious TEAE leading to death and the number of Serious TEAEs leading to death will be presented (Table 14.3.1.1).

All Serious TEAEs will be listed and all TEAEs leading to discontinuation will be listed (Table 14.3.2.1).

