2. RATIONALE

To date, CB-03-01 cream has been used for treatment of acne vulgaris for up to 12 weeks with no material safety issues to note. Given that acne vulgaris is a chronic condition which typically waxes and wanes over time and often requires extended (and sometimes intermittent) treatment, this study is designed to investigate the long-term safety of CB-03-01 cream, 1%.

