Over the course of the study, treatment on the face and/or trunk may be discontinued if/when acne clears (achieves an IGA of grade 0 or "minimal" grade 1) and re-instated if/when acne worsens (IGA \geq 2), according to the assessment of the investigator for each respective treatment area. If treatment is discontinued on face and trunk, all containers of the test article should be collected. If treatment is re-instated, sufficient test article will be dispensed to the subject; previously returned test article should NOT be re-dispensed, rather new containers of the test article will be dispensed as needed to the subject. Note: Subjects must be seen by the investigator via a scheduled or an unscheduled visit to change (i.e., restart or stop) the test article dosing on either treatment area (face and trunk). **If the subject feels that his/her acne has cleared, he/she should continue to apply the test article to the designated treatment area (face and/or trunk) as instructed by the investigator and call the investigator for an unscheduled visit. The subject should NOT change his/her dosing regimen until the investigator has documented acne clearance or significant worsening to support a change in the treatment.**

Subjects will be provided with a Subject Diary ([Appendix 2](#)) to record the dates and time of application, along with where the test article was applied. Subjects will be instructed to only apply the test article to the face and/or trunk as instructed by the investigator or designated study personnel. **Note: The dispensing, recording, and application of the test article by the subject may require adult supervision by the subject's parent/guardian.**

Subject and parent/guardian (if applicable) will be instructed to bring all the containers of cream (used and unused) and their completed diaries to each visit. The study staff will

weigh all the returned containers and will record the weights on the appropriate study medication accountability logs and case report forms (CRFs). Test articles that are returned should NOT be re-dispensed to the subject.

Subjects who are not compliant with applying the test article as instructed (determined from subject diaries and/or the weight of test article used) may be discontinued from the study.

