9. STUDY PROCEDURES

The study will consist of a Baseline Visit, follow-up visits at Months 1, 3, 6, and 9, and follow-up phone calls at Months 4.5 and 7.5. For subjects in the Phase 3 pivotal studies randomized to active (CB-03-01 cream, 1% twice daily), the total treatment period will be 12 (3+9) months; whereas for those subjects in the Phase 3 pivotal studies randomized to vehicle, the total treatment period will be 9 (0+9) months.

During the LTF study, treatment on face and/or trunk for a subject may be discontinued if/when acne is under successful control (achieves an IGA of grade 0 or "minimal" grade 1) and re-instated if/when acne worsens ($IGA \geq 2$), according to the assessment of the investigator for each respective treatment area. Subjects MUST be seen by the investigator via a scheduled or unscheduled visit to change (i.e., restart or stop) test article dosing).

Specific activities for each study visit are listed below.

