14. ADVERSE EVENT REPORTING

An **adverse event** (AE) is any untoward medical occurrence associated with the use of a drug in humans, whether or not considered drug related.

An AE (also referred to as an adverse experience) can be any unfavorable and unintended sign (e.g., an abnormal laboratory finding), symptom, or disease temporally associated with the use of a drug, without any judgment about causality. An AE can arise from any use of the drug (e.g., off-label use, use in combination with any drug) and from any route of administration, formulation, or dose, including an overdose.

Information on the medical condition of subjects should begin following the subject's written consent/assent to participate in the study and a medical history should be taken at screening. Other changes in subject health information becomes AE data when the subject begins dosing with the test article and therefore AE data should be collected from the date of the first dose of test article. These data are considered treatment-emergent AEs.

Timely and complete reporting of all AEs assists the contract research organization (CRO) in identifying any untoward medical occurrence, thereby allowing:

- 1) protection of the safety of study subjects;
- 2) a greater understanding of the overall safety profile of the test article;
- 3) recognition of dose-related test article toxicity;
- 4) appropriate modification of study protocols;
- 5) improvements in study design or procedures; and
- 6) adherence to worldwide regulatory requirements.

Test article is defined as a pharmaceutical form of an active ingredient or vehicle/placebo being tested or used as a reference in the study, whether blinded or unblinded. AEs may be either spontaneously reported or elicited during questioning and examination of a subject. All AEs must be completely recorded on the AE CRF. If known, the investigator should report the diagnosis of the underlying illness or disorder, rather than its individual symptoms. Subjects experiencing AEs that cause interruption or discontinuation of test article, or those experiencing AEs that are present at the end of their participation in the study should receive follow-up as appropriate. If possible, report the outcome of any AE that caused permanent discontinuation or that was present at the end of the study particularly if the AE is considered by the investigator to be treatment-related (i.e., definitely, probably, or possibly related to test article).

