Study endpoints that are SAEs (e.g., all-cause mortality) must be reported in accordance with the protocol unless there is evidence suggesting a causal relationship between the drug and the event (e.g., death from anaphylaxis). In this case, the investigator must immediately report the event to the Sponsor. In addition, such information should also be provided to the site’s respective IRB per their governing guidelines for SAE reporting.

If only limited information is initially available, follow-up reports are required. Should the investigator become aware of an SAE (regardless of its relationship to test article) that occurs within 30 days after stopping the test article, the SAE must be reported in accordance with procedures specified in this protocol. In the event of death, if an autopsy is performed, a copy of the report should be sent to the CRO, if available.

As required, the CRO will notify participating investigators of all suspected adverse reactions that are serious and unexpected. This notification will be in the form of an IND (and other national health authority) safety report of potential serious risks as soon as possible but no later than 15 calendar days after the Sponsor determines that the information is “reportable” according to the criteria listed in 21 CFR Section 312.32. These are:

- i) Serious and unexpected suspected adverse reactions,

- ii) Findings from other studies including epidemiological studies, pooled analyses, or other clinical studies that suggest a significant risk in humans exposed to the test articles,
- iii) Findings from animal or in vitro tests that suggest a significant risk to humans exposed to the test articles or reports of significant organ toxicity at or near the expected human exposure, and
- iv) Clinically important increases in the rate of occurrence of serious suspected adverse reactions.

Upon receiving such notices, the investigator must review and retain the notice with the Investigator Brochure and immediately submit a copy of this information to the responsible IRB according to local regulations. The investigator and IRB will determine if the informed consent/assent requires revision. The investigator should also comply with the IRB procedures for reporting any other safety information. Where required, submission of safety updates by the investigator to Health Authorities should be handled according to local regulations.

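### Cheap improvement: cream may be stopped for open-ended spells, yet TEAEs are reported only as crude percentages of everyone ever dosed, so risk while on cream is not shown

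*SAP*

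**What the plan says.** **Window.** SAP 7.9.2 defines TEAEs as "AEs occurring or worsening after the first dose of the test article". Protocol 14 agrees: "AE data should be collected from the date of the first dose of test article. These data are considered treatment-emergent AEs". Neither gives a closing rule based on last application, or a rule for events that start while cream is stopped.

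**Stopping.** Protocol 6.2 says "treatment on the face and/or trunk may be discontinued if/when acne clears", where clearing means IGA 0 or 1. Treatment may resume at IGA 2 or above, judged separately for face and trunk. No maximum time off is set. A change needs an in-person assessment: "Subjects must be seen by the investigator via a scheduled or an unscheduled visit to change (i.e., restart or stop) the test article dosing". Protocol 9 schedules "follow-up visits at Months 1, 3, 6, and 9, and follow-up phone calls at Months 4.5 and 7.5". Protocol 2 expects this pattern of use, since acne "often requires extended (and sometimes intermittent) treatment".

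**Summaries.** The Safety set (SAP 7.2) is everyone who applied cream at least once. SAP 7.9.2 plans subject counts, percentages and event counts. It plans no person-time rate and no split by whether the subject was on cream. Exposure in grams is summarised (SAP 7.8.2) and dose adjustments are listed (SAP 7.8.3), but neither is linked to adverse events.

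**The one post-treatment limit.** Protocol 14.2 applies to serious events only: if one "occurs within 30 days after stopping the test article, the SAE must be reported". The TEAE definition does not use it.

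**The concern.** TEAE incidence is the first safety endpoint (SAP 6.1.1). The objective (SAP 2.3) is the long-term safety of twice-daily cream, and the precision statement in SAP 6.3 refers to subjects exposed for 6 or 12 months. A subject can nevertheless stop at Month 1, stay clear and remain in follow-up to Month 9. That leaves 9 − 1 = 8 months off cream in which every new event is still treatment-emergent, while the subject counts fully in the denominator.

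Two separate consequences follow. Off-cream follow-up adds no opportunity for events that occur only during use, so a crude percentage falls below the risk under continued use. Background events arising off cream also enter the TEAE tables without being marked. A reader who wants the risk while using the cream cannot get it from the planned tables.

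**Working it through.** **1. The plan's own figures.** SAP 6.3 gives upper 95% limits of 3% (1% observed in 100 subjects) and 2.1% (1% observed in 300). With the stated formula, p + 1.96·√[p(1−p)/n]:

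- n = 100: 0.01 + 1.96·√(0.01·0.99/100) = 2.95%, stated as 3%.
- n = 300: 0.01 + 1.96·√(0.01·0.99/300) = 2.13%, stated as 2.1%.

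Both reproduce. They describe subjects exposed for the whole period, whereas SAP 7.5.3 counts subjects on-study.

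**2. What time off cream does to those limits.** Let g be the share of follow-up on cream. The documents do not give it, so all values of g below are assumptions. Keep the same event count, treat all events as on-cream, and replace n by n·g:

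| g | n = 100 | n = 300 |
|---|---|---|
| 100% | 2.95% | 2.13% |
| 90% | 3.28% | 2.36% |
| 75% | 3.93% | 2.83% |
| 50% | 5.88% | 4.24% |

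For example, at g = 75% and n = 100 there is 1 event in 75 subject-equivalents, so p = 1.33% and the limit is 3.93%.

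**3. An event caused only during use.** Assume a 3% risk over nine months of continuous use and a constant hazard: h = −ln(0.97)/9 per month. The crude percentage is 1 − exp(−9hg) = 1 − 0.97^g:

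- g = 80%: 2.41%
- g = 60%: 1.81%
- g = 40%: 1.21%

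**4. When events also occur off cream.** Assume an on-cream hazard of 0.40 per year, so the nine-month continuous-use risk is 1 − exp(−0.40·0.75) = 25.9%. Take g = 75%. The crude percentage is 1 − exp(−[0.40·0.75 + h_off·0.25]·0.75), and the off-cream share of events is 0.25·h_off / (0.40·0.75 + 0.25·h_off):

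| Off-cream hazard per year | Crude % | Ratio to 25.9% | Share of events off cream |
|---|---|---|---|
| 0 | 20.2% | 78% | 0% |
| 0.20 | 23.1% | 89% | 14% |
| 0.40 | 25.9% | 100% | 25% |

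Dilution therefore depends on the off-cream hazard being lower. With equal hazards the percentage is unchanged, but a quarter of the counted events arise off cream.

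**The case against.** Four stronger readings are tempting, and the documents do not support them.

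- **That the window never closes.** The definition has no end, but collection does. Adverse events are assessed up to Visit 10 (Day 274 ± 21), when the subject is discharged. Beyond that there is only the 30-day serious-event rule.
- **That counting off-cream events lowers the percentage.** It can only raise it. Any dilution comes from off-cream follow-up time, and only if the hazard is lower then.
- **That the crude percentage is invalid and the conclusion should rest on on-treatment rates.** Stop and restart is part of the design, and intermittent use is in the rationale. Incidence under that regimen answers a real question, and a crude proportion makes no claim about months of exposure.
- **That a drug pattern would be hidden.** SAP 7.9.2 plans related TEAEs and related serious TEAEs by SOC and PT. The causality categories in Protocol 14.1 use temporal sequence and, for the two strongest, improvement on stopping or reducing the dose. Local skin reactions are summarised by visit. These tables answer much of the worry about background events.

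The size is also uncertain. Stopping is optional and per area, a subject with a clear face may still treat the trunk, and stopping at Month 1 for good is an extreme case. Nothing in the documents shows that drug effects end soon after use.

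What remains is narrower. The related-event tables rest on open-label judgement and use the same denominator, so they do not give the risk while on cream. Exposure and dose-adjustment outputs are not linked to events.

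**Conclusion.** The point holds as a cheap improvement, not as an error in the planned tables. The open-ended definition, the unlimited time off cream and the absence of any on-treatment summary are all in the text. The planned percentage is valid for the as-used regimen but does not give the risk during use. For events confined to use it understates continuous-use risk roughly in proportion to time on cream. The illustration of 3% reading 2.4%, 1.8% or 1.2% rests on an assumed risk, assumed on-cream shares of 80%, 60% and 40%, a constant hazard and no carry-over. The actual effect cannot be sized from the documents and is nil for events with equal hazards on and off cream.

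**What to change.** In SAP 7.9.2:

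- Keep all planned TEAE tables.
- Flag each TEAE as on-treatment if its onset falls between the first application of a treatment period on either area and a stated lag after the last application of that period. Flag it as off-treatment otherwise. The protocol's 30-day serious-event window is a conventional choice of lag.
- Repeat Tables 14.3.1.1 and 14.3.1.2 for on-treatment TEAEs, adding subjects with an event per person-year on treatment. Count person-time over the same windows as the flag, up to the first event.
- Report these results beside the all-TEAE results when concluding on long-term safety, not in place of them.

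**Cost.** SAP wording and two repeat tables, with no change to clinical rules and no new data collection. Treatment periods must be derived from the subject diary and the dose-adjustment records (Protocol 6.2 and Appendix 3; SAP 7.8.3 and 7.8.4). This takes some programming, because Protocol Appendix 3 explicitly puts only the first and last application and dose modifications on the CRF.

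**Downsides to state in the SAP.** The lag is a convention and may misclassify delayed effects, which is one reason to keep the all-TEAE tables. Time on cream depends on response, so the rates weight towards poorer responders. A person-time rate assumes a roughly constant hazard.
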